8. CLINICAL EVALUATIONS AND PROCEDURES

8.1. Medical History

Medical history will include significant medical conditions, surgical history, and all medications, both prescription and nonprescription, taken within 14 days prior to screening. Exposure to SARS-CoV-2 infected individuals or patients with COVID-19 will be documented.

8.2. SARS-CoV-2 Infection Assessment

Ordinal Scale for Clinical Improvement: A nine point scale will be used to assess the severity of COVID-19 which has been derived from the draft scale proposed by WHO.⁹

The following table will be used to assess symptoms due to SARS-CoV-2 infection:

Table 2: SARS-CoV-2 Infection Symptom Score

Symptom	Score (0-3)
Cough	
Shortness of breath or difficulty breathing	
Muscle aches or fatigue	
	Score (0-4)
Fever	

Symptom Scores (Cough, Shortness of breath or difficulty breathing, Muscle aches or fatigue)

- 0- None
- 1- Mild (occasional or not bothersome)
- 2- Moderate (frequent or bothersome)
- 3- Severe (interferes with daily activities)

Note: Fever will be scored based on temperature recorded as part of vital signs and graded according to the Toxicity Grading Scale for Healthy Adult and Adolescent Volunteers Enrolled in Preventive Vaccine Clinical Trials:

٠	0	No Fever
٠	1- Mild	38.0-38.4°C/100.4-101.1°F
•	2-Moderate	38.5-38.9°C/101.2-102.0°F
•	3-Severe	39.0-40.0°C/102.1-104.0°F

• 4-Life Threatening $> 40.0^{\circ}C/>104.0^{\circ}F$

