7.7. Schedule of Study Activities

The schedule of events is presented in Table 1.

Table 1:Schedule of Events

Event	Screening	Dose 1 ^a	Dose 2, 3, 4 ^a	Follow-up/Early Discontinuation from Study	Study Completion
	V1	V2	V3, 4, 5	V6	V7
	Day -2 to Day 1	Day 1 ^b	Days 3, 6, 10	Day 15	Day 29
Informed consent	X				
Medical history	Х				
Pregnancy test ^c	Х			Х	Х
Physical exam	Х	Х	Х	Х	
Vital signs ^d	Х	Х	Х	X	
Spirometry ^e	Х	Х	Х		
Symptom score ^f	Х	Х	Х	X	Х
SARS-CoV-2 test ^g		Х		X	Х
Study drug administration ^h		Х	Х		
Adverse events	Х	Х	Х	X	Х
Concomitant medications	Х	Х	Х	X	Х
Ordinal Scale for Clinical Improvement	X	Х	Х	Х	Х
Randomization	Х				

^a Vital signs, adverse events, and concomitant medications will be assessed prior to administration of study medication and also at 30 minutes post-dose.

^b There is no Day 0 in this study

^c Urine pregnancy test or serum pregnancy test if women are of child-bearing potential. If urine pregnancy test is positive, a serum pregnancy test must be done. Pregnancy test is required for Early Discontinuation, not Day 15.

^d Vital signs will include body temperature, blood pressure measurements, heart rate, and respiratory rate.

^e Spirometry will be done at screening to document eligibility. On days of dosing, spirometry will be done pre-dose and at 30 minutes (± 15) minutes post-dose. If the FEV1 is reduced > 10% compared to the pre-dose baseline the FEV1 should be repeated as clinically indicated

^fSARS-CoV-2 symptoms will be assessed at each visit according to the Symptom Score

^g SARS-CoV-2 testing will be performed pre-dose on Day 1 (Visit 2), Day 15 (Visit 6) and at Day 29 (Visit 7). Additional testing should be conducted at any point during the study when clinical symptoms are suggestive of potential COVID-19.

^h Study drug administration must be done by a health care professional

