7.13. Early Discontinuation from Dosing and Study Withdrawal

Subjects who have received at least one dose of investigational treatment and are discontinued from dosing should continue to the final assessment at Day 29 according to the schedule of events specified for pre-dose assessments. There will be no post-dose assessments for these subjects.

Should the subject's study participation end prior to the completion of Study Day 15, the following assessments will be conducted as soon as possible after the decision to withdraw from the study is made.

- Physical examination
- Vital signs
- Serum pregnancy test or urine test (if urine test is positive, a serum test must be conducted)
- Nasaopharyngeal or oropharyngeal sample for SARS-CoV-2 testing
- Adverse event assessment
- Concomitant medication assessment

- SARS- CoV-2 infection symptom score
- Ordinal Scale for Clinical Improvement

7.14. Study Completion Day 29

Assessments should occur within +2 days of target Study Day.

- Serum pregnancy test or urine test (if urine test is positive, a serum test must be conducted)
- SARS- CoV-2 Symptom Score
- Adverse event assessment
- Concomitant medication assessment
- Ordinal Scale for Clincal Improvement
- Nasaopharyngeal or oropharyngeal sample for SARS-CoV-2 testing

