8.3. Physical Examination and Vital Signs

A qualified medical person will perform a physical examination at all indicated visits.

- Physical examination: general appearance, head, eyes, ears, nose, throat, neck, cardiovascular, lungs, abdomen, lymph nodes, extremities, neurological, skin, musculoskeletal, and other.
- Vital signs will include body temperature, blood pressure, heart rate, and respiratory rate.

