The number and percentages of subjects in each severity category of the 9-point Ordinal Scale will be presented by visit and treatment group.

Graphical illustrations of the Ordinal Scales through Day 29 will be presented using stacked bar chart for each treatment group. The X axis representing time points and Y axis representing the cumulative number of subjects for each Ordinal Scale. Each bar is divided into a number of subbars stacked end to end corresponding to different Ordinal Scales.

The changes in Ordinal Scales through Day 29 will be examined using box and whisker plots for each treatment group. The X axis representing the post-baseline time points and the Y axis representing the change from baseline in Ordinal Scales at each post-baseline visit.

Symptom Score

The symptoms due to SARS-CoV-2 infection will be assessed and the symptom scores (Cough (0-3), Shortness of breath or difficulty breathing (0-3), Muscle aches or fatigue (0-3), Fever (0-4)) will be recorded in the eCRF.

The respiratory symptom score will be calculated by summing the symptom scores from Cough and Shortness of breath or difficulty breathing. The total symptom score will be calculated by summing all symptom scores.

The scores from each symptom together with calculated respiratory symptom scores and total symptom scores will be summarized by presenting the number and percentage of ITT subjects for each category by visit and treatment group.

Each symptom score (Cough, Shortness of breath or difficulty breathing, Fatigue, Fever, Respiratory, Total) from each post-baseline timepoint will be compared between treatment groups using non-parametric Wilcoxon Rank Sum test at 2-sided alpha level of 0.1. The p-value will be presented at each post-baseline visit.

A radar plot will be created by presenting each symptom score in group mean at each time point by treatment group.

Subjects requiring ICU admission

Subject data pertaining to ICU admission will be recorded in the database.

The proportion of ITT subjects who are admitted to the ICU from Day 1 to Day 29 within each

treatment group will be presented along with a two-sided exact (Clopper-Pearson) 90% confidence interval (CI).

The observed difference in the proportion of subjects requiring ICU admission between treatment groups along with the exact unconditional 90% CI for risk difference will be calculated. The null hypothesis will be tested using Fisher's exact method and the p-value will be reported.

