11. APPENDIX

11.1 Appendix A: Schedule of Events

Event	Screening	Dose 1ª	Dose 2, 3, 4 ª	Follow-up/Early Discontinuation from Study	Study Completion
	Vl	V2	V3, 4, 5	V6	V 7
	Day -2 to Day 1	Day 1 ^b	Days 3, 6, 10	Day 15	Day 29
Informed consent	Х				
Medical history	Х				
Pregnancy test ^c	X			Х	Х
Physical exam	Х	X	Х	Х	
Vital signs ^d	Х	Х	Х	Х	
Spirometry ^e	Х	X	X		
Symptom score ^f	Х	Х	Х	X	Х
SARS-CoV-2 test ^g		Х		Х	х
Study drug administrationh		X	Х		
Adverse events	Х	Х	Х	Х	Х
Concomitant medications	X	X	Х	Х	Х
Ordinal Scale for Clinical Improvement	x	Х	Х	x	Х
Randomization	X				

^a Vital signs, adverse events, and concomitant medications will be assessed prior to administration of study medication and also at 30 minutes post-dose.

^b There is no Day 0 in this study

^c Urine pregnancy test or serum pregnancy test if women are of child-bearing potential. If urine pregnancy test is positive, a serum pregnancy test must be done. Pregnancy test is required for Early Discontinuation, not Day 15.

d Vital signs will include body temperature, blood pressure measurements, heart rate, and respiratory rate.

^e Spirometry will be done at screening to document eligibility. On days of dosing, spirometry will be done pre-dose and at 30 minutes (±15) minutes post-dose. If the FEV1 is reduced > 10% compared to the pre-dose baseline the FEV1 should be repeated as clinically indicated

f SARS-CoV-2 symptoms will be assessed at each visit according to the Symptom Score

^g SARS-CoV-2 testing will be performed pre-dose on Day 1 (Visit 2), Day 15 (Visit 6) and at Day 29 (Visit 7). Additional testing should be conducted at any point during the study when clinical symptoms are suggestive of potential COVID-19.

^h Study drug administration must be done by a health care professional

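### The Day 29 fever item, and the total symptom score that includes it, have no scheduled temperature behind them

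*Protocol*

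**What the plan says.** Protocol Section 8.2 (Table 2) defines a four-item symptom score: cough, shortness of breath, and muscle aches or fatigue, each scored 0 to 3, and fever, scored 0 to 4. For fever it adds: "Fever will be scored based on temperature recorded as part of vital signs". Section 8.3 makes temperature part of that procedure: "Vital signs will include body temperature, blood pressure, heart rate, and respiratory rate". Footnote d to Protocol Table 1 says the same.

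On timing, footnote f to both schedules reads: "SARS-CoV-2 symptoms will be assessed at each visit according to the Symptom Score". The Day 29 list in Protocol Section 7.14 includes the "SARS- CoV-2 Symptom Score". The other entries there are a pregnancy test, adverse events, concomitant medications, the ordinal scale and a swab. Vital signs and temperature are not on the list. The vital-signs row of Protocol Table 1 and of SAP Appendix A stops at Day 15.

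On analysis, SAP Section 2.2.2 lists the symptom score among the secondary efficacy endpoints. Section 6.2 defines the total as the sum of all the items and then states: "Each symptom score (Cough, Shortness of breath or difficulty breathing, Fatigue, Fever, Respiratory, Total) from each post-baseline timepoint will be compared between treatment groups". The method is the "non-parametric Wilcoxon Rank Sum test at 2-sided alpha level of 0.1".

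**The concern.** Two of the planned Day 29 comparisons rest on a measurement that the visit does not include. The fever grade is a banding of a recorded temperature, so it cannot be assigned as specified without one. The total cannot be formed as defined without the fever grade.

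Day 29 is also the visit that closes the 28-day observation period. If the plan is silent, sites may handle the fever field differently, and neither document has a rule that would make the handling uniform or visible to the analyst.

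**Working it through.** No power, alpha or sample-size figure is involved. The check sets the passages side by side and counts the affected comparisons.

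**Step 1. Is there any other source for fever?** Protocol Section 8.2 names vital-sign temperature only. No section of either document provides for self-report, a home thermometer or recall.

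**Step 2. Which visits have both the score and a temperature?**

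| Visit | Symptom score | Vital signs |
|---|---|---|
| Screening (Protocol 7.9) | yes | yes |
| Day 1 pre-dose (7.10.1) | yes | yes |
| Days 3, 6, 10 pre-dose (7.11.1) | yes | yes |
| Day 15 (7.12) | yes | yes |
| Early discontinuation (7.13) | yes | yes |
| Day 29 (7.14) | yes | **no** |

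Day 29 is the only visit where the pairing breaks. Section 7.14 is a plain list and agrees with both schedule tables, so a table damaged in conversion does not explain the gap.

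**Step 3. How many planned tests does this touch?**
- Scores tested (SAP 6.2): cough, shortness of breath, fatigue, fever, respiratory, total = 6.
- Post-baseline visits with a symptom score: Days 3, 6, 10, 15, 29 = 5.
- Planned comparisons: 6 × 5 = 30.
- Comparisons that need a Day 29 temperature: Fever and Total = 2, so 2/30, or about 7%.
- Day 29 comparisons that do not need one: 6 − 2 = 4 (cough, shortness of breath, fatigue, and respiratory, which sums the first two).

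**Step 4. What happens to the total if fever is absent?** As defined, its maximum is 3 + 3 + 3 + 4 = 13. If the three remaining items were summed instead, the maximum would be 3 + 3 + 3 = 9, and the Day 29 value would not be on the same scale as earlier visits. The SAP gives no rule for a partial total.

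**Step 5. Does another SAP rule fill the gap?** Section 4.4 leaves missing values missing, apart from survival censoring and partial dates for medications and adverse events. Section 4 keeps unscheduled visits out of the summaries, so a temperature from an unscheduled visit would not enter the Day 29 tables. Neither rule supplies a value.

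**The case against.** The strongest reply is that the score itself is required at Day 29 and fever is one of its items, so a site completing the form would have to take a temperature, and nothing forbids it. That is fair. A reader might infer from the schedules that Day 29 has no fever data at all, or that the two tests cannot be carried out. The documents do not support that. They show only that no temperature is scheduled. The eCRF and its completion instructions are not among the documents and may contain a temperature field. For the total, three of the four items are collected normally.

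A reader might also infer that sites would enter 0 for fever without measuring it and that this would bias the total toward no difference. Neither step is established. The documents do not say what sites would enter, and they give no Day 29 fever rates. If few subjects are febrile by then, setting fever to 0 changes almost nothing. If the arms differed on fever in the opposite direction to the other items, removing fever could enlarge the difference in the total.

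The last part of the reply concerns weight. The symptom score is not named in the protocol's secondary objectives and appears as an endpoint only in the SAP. SAP Section 4.5 calls the study exploratory and makes no multiplicity adjustment. Fever and Total remain supported at Days 3, 6, 10 and 15. All of this stands and limits the importance of the point. It does not remove the inconsistency between the required score and the scheduled procedures, which appears in three places.

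**Conclusion.** The inconsistency is real and narrow. Fever is graded from vital-sign temperature, the score is due at Day 29, and no vital signs or temperature are scheduled then. Two of the 30 planned symptom comparisons therefore lack a scheduled input, for every subject who reaches that visit. The Day 29 by-visit frequency tables for fever and total share the gap, as does the fever value in the radar plot.

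Followed as written, the affected values would be missing under SAP Section 4.4, or would be present only where a site chose to take a temperature. The conclusion assumes that the schedules and Section 7.14 are the full list of Day 29 procedures. No direction or size of bias can be claimed.

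The primary ordinal-scale endpoint does not use the fever score. The point should be corrected because it concerns a listed secondary efficacy endpoint and is cheap to put right. It does not threaten the trial's main conclusion.

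**What to change.** Add body temperature (or the full vital-signs procedure) to the Day 29 column of Protocol Table 1, to the list in Protocol Section 7.14, and to SAP Appendix A. The cost is one extra reading at a visit that already includes a swab, plus matching wording in the three places.

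If Day 29 visits have already taken place and this is no longer possible, amend SAP Section 6.2 so that the Fever and Total comparisons cover only visits with scheduled vital signs, that is, Days 3, 6, 10 and 15. That gives up 2 of the 30 tests and leaves 28, with the other four scores still compared at Day 29.

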8.3. Physical Examination and Vital Signs

A qualified medical person will perform a physical examination at all indicated visits.

- Physical examination: general appearance, head, eyes, ears, nose, throat, neck, cardiovascular, lungs, abdomen, lymph nodes, extremities, neurological, skin, musculoskeletal, and other.
- Vital signs will include body temperature, blood pressure, heart rate, and respiratory rate.

8.4. SARS-CoV-2 Testing

All testing associated with the conduct of the study will be conducted at a central laboratory designated by the Sponsor. At every sampling time point, a nasopharyngeal swab or an oropharyngeal swab will be taken. Directions for specimen collection, handling and transport will be provided in the Laboratory Manual.

8.5. Spirometry

American Thoracic Society or British Thoracic Society guidelines should be followed in the conduct of spirometry assessments performed at screening.

9. DESCRIPTION OF STUDY TREATMENT

9.1. Placebo

Sterile saline for inhalation will be used as the placebo.

9.2. PUL-042 Inhalation Solution

Additional information concerning PUL-042 including receipt, storage, preparation, and time windows for preparation and subject administration will be provided in the Pharmacy Manual.

The teratogenic effects of PUL-042 are unknown.

9.2.1. PUL-042

The investigational product, PUL-042 Inhalation Solution, is a combination of Pam2CSK4 acetate and ODN M362 sodium (4:1 molar ratio [Pam2:ODN]). PUL-042 is formulated as a solution in SWFI, USP, with no other excipients, at a pH of 5 to 8. Pam2 is a synthetic 6-amino acid lipopeptide, and ODN is a synthetic 25-base, single-stranded phosphorothioate oligodeoxynucleotide. The structure of Pam2 and the nucleotide sequence of ODN are shown in Section 5.2 (Figure 3).

The investigational product components (Pam2CSK4 and ODN M362 sodium) are manufactured by: Albany Molecular Research (Glasgow) Ltd. [name].

9.3. Packaging and Labeling

PUL-042 will be packaged as separate component solutions of Pam2 and ODN in 5-mL Type I sterile glass vials or 2-mL Type I sterile glass vials, sealed with a rubber injection stopper and an aluminum tear-off overseal. PUL-042 components will be manufactured, labeled, and packaged under Good Manufacturing Practice guidelines. Sterile saline for inhalation will be supplied by the investigative site.

9.4. Shipment and Storage

Individual components of PUL-042, Pam2 Solution and ODN Solution, are stored frozen $(-20 \pm 5^{\circ}C)$ at the drug distribution center and will be shipped to the site on dry ice.

Cartons containing 5-mL or 2-mL glass vials of individual PUL-042 components (Pam2 and ODN) will be sent to the clinical study site pharmacy. The study drug components will be stored frozen (-20 \pm 5°C) at the study site until ready for use.

9.5. Preparation and Administration

The pharmacist at the clinical site will be responsible for the preparation of the appropriate concentration of PUL-042 by dilution of the components of PUL-042 in SWFI. Specific instructions will be provided for the preparation of PUL-042 Inhalation Solution in the Pharmacy Manual. PUL-042 Inhalation Solution must be administered within 4 hours of preparation.

10. CONCOMITANT MEDICATIONS, TREATMENTS, AND PROCEDURES

All concomitant medications, including prescription and nonprescription over-the-counter drugs, vitamins, or nutritional supplements, taken during the 14 days prior to screening or while a participant is on study will be recorded in the electronic case report form (eCRF). Documentation will include start and stop dates and reasons for use.

Any diagnostic, therapeutic, or surgical procedures performed during the study period will be documented.

11. STUDY WITHDRAWAL

11.1. Study Termination

The entire study may be terminated at any point based on the evaluation of the study or development program by Pulmotect. A Data Safety Monitoring Board (DSMB) will review unblinded data on the first 40 subjects then again at 80 subjects and 120 subjects with additional ad hoc reviews at the request of the DSMB. The DSMB can also request that study enrollment be paused at any time should enrollment be faster than anticpated such that adequate safety review is not able to occur between the specified review meetings.

11.2. Subject Withdrawal/Lost to Follow-up

Subjects who are discontinued from dosing during the study and have received at least one dose of investigational treatment must be followed to Day 29 according to the schedule of events specified above for pre-dose assessments. There will be no post-dose assessments for these subjects.

Subjects will be free to withdraw from the study at any time without giving a reason. Subjects will be considered withdrawn from the study in the event of any of the following reasons:

- Withdrawal of the subject's consent for any reason.
- Subject lost to follow-up prior to the Study Day 29 assessments.

In the event a subject withdraws from the study for any reason, the Investigator must notify Pulmotect as soon as possible and complete the applicable eCRF pages. An effort should be made to capture the reason(s) for withdrawal.

Subjects that withdraw should complete the Early Discontinuation assessments as soon as possible.

A subject is considered lost to follow-up after 3 documented attempts to contact the subject without success.

Subjects who withdraw after the start of study drug administration will not be replaced.

12. ADVERSE EVENTS

Adverse events will be described and graded according to the Toxicity Grading Scale for Healthy Adult and Adolescent Volunteers Enrolled in Preventive Vaccine Clinical Trials.

Symptoms and events associated with SARS-CoV-2 infection will be scored as per the SARS-CoV-2 infection symptom score (Table 2) and the Ordinal Scale for Clinical Improvement (Table 4). These findings should not be reported as Adverse Events.

